Genes that were differentially expressed between groups were selected for mediation analyses. Diagnosis by BMI effects on expression of dopamine genes were fully mediated by expression of INSR. Analysis of conditional indirect effects showed interactions between INSR and BMI, indicating significantly stronger indirect effects at higher BMI values. In the hippocampus, we observed that expression of insulin receptor substrate 1 and 2 fully mediated the effects of diagnosis on expression of dopamine genes (Figure 2). All models were significant (e.g. DRD1: $R^2 = 0.31$, $F_{6,385} = 29.519$, p < 0.001). These results suggest that the differential expression of dopamine-related molecules in the postmortem brain of individuals with mental disorders is related to altered expression of insulin signaling genes. We also observed that obesity has region-specific moderating effects on gene expression and co-expression, supporting the hypothesis that metabolic systems are critical mediators of dopaminergic function and providing the rationale for further investigation.

Figure 1 – Mean standardized expression values of insulin and dopamine signaling genes in the dorsolateral prefrontal cortex, according to group (HC vs. MI) and obesity (BMI \geq 30 kg/m²). HC: healthy controls; MI: mental illness; BMI: body mass index.

[figure not shown]
[figure not shown]

Figure 2 – Unstandardized path coefficients for a mediation model in the hippocampus, adjusted for age, gender, race, ethanol and nicotine/cotinine. * p < 0.05; ** p < 0.001.

[name] Research Proposal Project Title: Anhedonia and the insulin pathway: a mechanistic nexus for the mood and metabolic disorders comorbidity

3. Design and Methodology

Study population: We propose to recruit 50 adults between the ages of 18 to 50 years: 25 patients with DSM-5 defined MDD or BDI/II, in a depressive episode, recruited from the Mood Disorder Psychopharmacology Unit, University Health Network, and 25 age- and sex-matched healthy controls recruited through local advertisements in the community.

Inclusion criteria (patients):

- 1. Age 18-50
- 2. DSM-5 defined MDD/BD and a total score ≥20 on the Montgomery-Åsberg Depression Rating Scale (MADRS) and no history of dementia or intellectual disability
- 3. A written, voluntary informed consent prior to study enrollment

Exclusion criteria (patients):

- 1. Use of insulin and/or oral hypoglycemiants, due to its confounding effects

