- 2. Diagnosis of possible or probable AD, MCI, or any other dementia
- 3. History of neurological disorder, or evidence of neurologic or other physical illness that could produce cognitive deterioration
- 4. Substance use disorder within 3 months before screening or a positive baseline toxicology screen
- 5. Presence of clinically unstable general medical illness
- 6. Pregnancy or breastfeeding
- 7. MRI contraindications

Inclusion criteria (healthy controls):

- 1. Age 18-50
- 2. A written, voluntary informed consent prior to study enrollment

Exclusion criteria (healthy controls):

- 1. Use of insulin and/or oral hypoglycemiants, due to its confounding effects
- 2. Presence of any current or lifetime psychiatric or neurological conditions
- 3. Substance use disorder within 3 months before screening or a positive baseline toxicology screen
- 4. Presence of clinically unstable general medical illness
- 5. Pregnancy or breastfeeding
- 6. MRI contraindications

Study Procedures: Single-dose, randomized, controlled, double-blinded, cross-over study (50 participants)

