After screening and baseline assessment, participants will receive a crossover treatment assignment of either insulin or diluent followed by an MRI scan, with a washout period of 1 week. Therefore, participants will receive a total of 2 MRI scans throughout the course of the study- one following the first treatment, and one following the second treatment. The subsample will be enriched for the presence of self-reported anhedonia, using a score of greater than 2 on the SHPS as a cut-off, which provides the best discrimination between "normal" and "abnormal" level of hedonic tone⁸¹. This subsample will also have equal representation of normal weight and obese participants.

To proxy insulin activity within pre-selected brain regions, we will use a provocation paradigm, involving the administration of exogenous intranasal insulin, based on the published work of other research groups research groups Activation of brain regions will be assessed during the resting state and task-based reward paradigm (i.e. EEfRT), following an intranasal administration of either 160 units of intranasal insulin or diluent (insulin and placebo will be prepared as nasal sprays), in a randomized, double-blinded, cross-over design. Please refer to the pharmacy manual for randomization details. A hypothesis-driven region of interest approach will be used to investigate initially the striatum and the medial PFC (mPFC). Willingness to make effort for rewards will be measured with the EEfRT³³. Briefly, participants have to select between an easy and a hard task. Both tasks involve pressing a key for a predetermined amount of time. The hard task offers more money (variable amounts), but is harder and takes twice as long. Participants make their selection knowingly under different win probabilities (i.e. they might not win money even if they are successful if the win probabilities are low). This task will measure proportions of hard-task choices with varying probabilities of reward and reward magnitudes. To provide stable estimations, the fMRI task will be conducted in three runs⁷³.

Table 1

Assessment	Baseline (V1)	First Spray (V2)	Second Spray (V3)		
General Information					
Demographics	✓				
Questionnaire					
Medical Comorbidity	✓				
Questionnaire					
Family Psychiatric	✓				
History					
Questionnaire	,				
SES Questionnaire	√				
MRI Questionnaire	✓	✓	✓		
Anthropometric Measures					
Height (ft)	✓				
Weight (kg)	✓	✓	✓		
Blood Pressure	✓	✓	✓		
(mmHg)					

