4.3 Disposition of Used/Unused Product

Please refer to the pharmacy manual for information on the disposition of used/unused product.

5. Methods of Assigning Subjects to Treatment Groups

Please refer to the pharmacy manual for information on the methods of assigning subjects to treatment groups (i.e. randomization, and blinking/masking).

6. Analytic Plan, Power Analysis and Approach to Potential Challenges

Initial data analyses will inspect socio-demographic and clinical group differences as well as correlations between clinical and biological variables and specified behavioral measures. Clinical or demographic variables demonstrating a correlation with both biological and behavioral measures, will be assessed as potential confounders⁸². The EEfRT behavioral data will be analyzed using generalized estimating equation (GEE) models, according to previous studies^{30,33}. For the assessment of associations between the remaining behavioral measurements and biometric data, we will use generalized linear models, due to its greater flexibility and ability to analyze data with non-normal distributions. Group (mood disorders vs. non-psychiatric) effects will be analyzed, with age, gender, and other relevant covariates included in the models. Special considerations will be given to smoking and use psychotropic medications, given its potential effects of both reward processes and insulin signaling.

Mediation and moderation models will be assessed using regression-based, bias-corrected bootstrap tests⁸³. The main objective is to test whether there is a mediated effect of X (i.e. mood disorders) on the outcome Y (i.e. anhedonia and reward behavior) through M (i.e. insulin signaling and dopamine metabolism). If appropriate, moderated mediation models (conditional process analysis) will be used to test whether the mediation effect was contingent on a moderating variable W (e.g. obesity, medications). This method uses bootstrapping to determine bias-corrected (asymmetric) 95% confidence intervals for the indirect effects⁸⁴. Bootstrapping methods have been recently advocated, as they are based on random sampling of the data and do not make assumptions about the shape of the sampling distribution; they are also more powerful and allow for the construction of more accurate confidence intervals, relative to normal theory methods⁸³.

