For the imaging analysis, statistical parametric mapping (SPM8, Wellcome Department of Cognitive Neurology, London, U.K., www.fil.ion.ucl.ac.uk/spm) will be used to preprocess the raw fMRI data. A hypothesis-driven region of interest approach will be used to investigate initially the striatum and mPFC. For the resting-state data, BOLD signal in these regions will be compared between conditions (i.e. insulin and placebo) for each subject using GEE. For the task-based data, mean percent BOLD signal change in these regions under varying reward and probability conditions will be extracted, and we will compute a set of contrasts testing the main effects of reward magnitude, reward probability, and the interaction for each subject⁷³. These first-level individual contrast maps will be fed into a second-level group (i.e. mood disorders vs. controls) and condition analysis, which will also use GEE. Association between behavioral measurements, biometric data and neuroimaging measurements will be assessed with generalized linear models. The false discovery rate (FDR) method will be used to correct for multiple comparisons and significance will be taken at a FDR-corrected threshold of p < 0.05^{86} .

Power Analysis: The primary hypothesis of this study is that anhedonic symptoms in individuals with mood disorders will be mediated by abnormalities in insulin signaling; therefore, the power analysis is based on a bias-corrected bootstrap test of mediation. Results from our preliminary data indicated that the path coefficients were mostly of medium effect sizes (e.g. $\beta \approx 0.25$ -0.35); empirical analysis indicated that in this condition a sample sizes of 116 is necessary to achieve 80% power85. To account for the possibility of subject attrition and/or inadequate measurements, we will set an initial enrollment goal of 150 subjects.

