Potential Challenges and Ways to Overcome Them: The primary challenge in this study is that of recruiting and retaining 150 participants over a 3-year period. Given the experience and volume of the mood disorders clinics involved in this study, we believe that this goal is attainable. There are two potential limitations in our sample composition proposal. First, it is expected that the majority of participants recruited in tertiary mood disorders clinics will report clinically significant anhedonic symptoms. Nonetheless, it is possible that some of the subconstructs analyzed will not display satisfactory psychometric properties for contrast/comparisons. Second, we propose to pre-stratify our sample based on overweight/obesity. There is a well-documented association between adiposity and insulin sensitivity; though these are not perfectly collinear constructs. There are no, however, validated, publicly available, normative data of anhedonic symptoms, whereas gold-standard evaluations of insulin sensitivity are invasive and costly (e.g. hyperinsulinemic euglycemic clamp); therefore approximations are initially necessary. We propose to conduct a preliminary analyses after one third of the sample (n=50) is recruited and reevaluate the sample selection procedures.

A key challenge for the interpretation of results will be how to account for the role of potential confounding factors. These factors include, but are not limited to, psychotropic medications, smoking, socio-demographic characteristics, dietary and lifestyle factors. We opted for a "real-life" naturalistic treatment-seeking sample, as we seek to recruit a sample that is representative of other clinical samples. Moreover, ethical considerations preclude us from withdrawing or deferring initiation of medications. Therefore, we propose to systematically measure these confounding factors and use it as control and/or sub-stratification variables, as appropriate.

ADVERSE EVENTS

Definitions

Adverse event

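### Section 3 recruits 50 people in total; Section 6 needs 116 and enrols 150. No power is given for 50, where the mediation test would have roughly 26–60%.

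*Combined protocol and SAP*

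**What the plan says.** Section 3 (Design and Methodology), Study population: "We propose to recruit 50 adults between the ages of 18 to 50 years". They are 25 patients in a depressive episode and 25 matched healthy controls. Study Procedures in the same section gives the same number for the design: "Single-dose, randomized, controlled, double-blinded, cross-over study (50 participants".

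Section 3, Neural Circuits Assessment, then uses a different term for the scanned participants: "The subsample will be enriched for the presence of self-reported anhedonia". It gives neither the size of this subsample nor the sample it is drawn from.

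Section 6, Power Analysis, bases the calculation on a bias-corrected bootstrap test of mediation with path coefficients of about 0.25–0.35. It states that "a sample sizes of 116 is necessary to achieve 80% power" and, to allow for attrition or inadequate measurements, "we will set an initial enrollment goal of 150 subjects". Potential Challenges in the same section repeats the larger figure: "The primary challenge in this study is that of recruiting and retaining 150 participants over a 3-year period". It also plans a preliminary analysis at n=50, described as a third of the sample, to review how participants are selected.

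On the test itself, Section 6 says "The main objective is to test whether there is a mediated effect of X (i.e. mood disorders", with insulin signalling and dopamine metabolism as mediators and anhedonia and reward behaviour as outcomes. Group effects are to be analysed "with age, gender, and other relevant covariates included in the models".

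**The concern.** Total enrolment is a basic design fact, and the two values differ threefold. The figures 116 and 150 agree with each other, since 150 is 116 plus an allowance for loss. The conflict is between 50 and that pair. The only power statement therefore belongs to a sample that Section 3, as written, does not recruit.

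If 50 is the total, three things follow:

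- The test behind the stated primary hypothesis has far less than the advertised 80% power, and nothing in the document warns the reader.
- The preliminary analysis at n=50 falls at the end of recruitment, so it cannot change the sample selection it is meant to review.
- The crossover adds no people to the mediation contrast, because X is diagnosis, a between-person factor.

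A secondary point is that the primary hypothesis is worded in two ways. Section 1 (Hypothesis and Specific Aims) has an effort deficit associated with insulin measures. Section 6, Power Analysis, has anhedonic symptoms mediated by insulin signalling.

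**Working it through.** **Inputs from the plan.** Section 3: N = 50, split 25:25. Section 6: N = 116 for 80% power, 150 enrolled, paths 0.25–0.35, bias-corrected bootstrap, 95% confidence interval (so two-sided 5%). The plan does not say which pair of paths lies behind 116.

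**Simple ratios.**

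- 50/116 = 0.431, so 50 is 43% of the number called necessary.
- 116/150 = 0.773, an implied loss of 22.7% (no rate is stated).
- The same loss from 50 leaves 50 × 0.773 = 38.7, about 39.
- 50/150 = one third, which matches the preliminary-analysis text only if the total is 150.

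**Model simulated.** M = aX + e₁ and Y = bM + c′X + e₂. X is binary and evenly split, paths are standardised, and there is one mediator. The base case has c′ = 0, no covariates and one value of M and Y per person. The test rejects when the 95% bias-corrected bootstrap interval for a·b excludes zero. Base cells at n = 39 and 50 used 7,000 datasets with 1,000 bootstrap draws (Monte Carlo standard error about 0.5–0.6 points). The 0.25/0.35 pair at n = 116 used 6,000 datasets.

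**Step 1: reproduce 116.** At n = 116, power is 82% for a = 0.25, b = 0.35 and 77% for a = 0.35, b = 0.25. The stated 80% is reproduced for that pair.

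**Step 2: power at 50 and 39.**

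| Evaluable n | both 0.25 | both 0.30 | both 0.35 | one 0.25, one 0.35 |
|---|---|---|---|---|
| 116 | 66–69% | 83–87% | 94–96% | 77–82% |
| 50 | 26% | 42% | 60% | 38–39% |
| 39 | 18% | 30% | 45% | 28–30% |

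The equal-path cells in the 116 row are ranges over ways of scaling the paths and over binary or continuous X. Repeat runs of the n = 50 base case gave 25–26%, 42–43% and 58–60%. With unit residual variances instead of standardised paths, n = 39 gives 17% (0.25) and 41% (0.35).

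**Step 3: sensitivity, equal paths from 0.25 to 0.35** (assumed scenarios, not taken from the plan).

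| Scenario | n = 50 | n = 39 |
|---|---|---|
| Two covariates unrelated to X, M, Y | 24–55% | 15–40% |
| Four such covariates | 21–51% | 14–36% |
| Direct effect c′ = 0.25 | 28–63% | 18–49% |

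The covariate cells used 2,500 datasets (standard error about 1 point) and the c′ cells 5,000.

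**Step 4: what 80% would need.** At n = 50, power is 79.5% with both paths at 0.42 and 81.2% at 0.43. At n = 39 it is 79.4% at 0.47 and 81.4% at 0.48. Both lie above the plan's 0.25–0.35.

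**Step 5: does accrual settle the total?** Section 7 (Anticipated Timeline) gives 27 months at 2–3 per site per month: 27 × 2 = 54 to 27 × 3 = 81 per site. Overall, 50 needs 50/27 = 1.9 per month and 150 needs 150/27 = 5.6. The number of sites does not appear in the text available, so this does not decide it.

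**The case against.** The strongest reply is that the numbers can be made compatible. Fifty is exactly a third of 150, Section 3 uses the word subsample, and Section 6 speaks of clinics in the plural. Two sites would accrue 108–162 over 27 months, which covers 150. Section 3 might therefore describe an imaging stage of a 150-person study. In that case the percentages at 50 would not describe the primary test.

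That reading is possible, but the plan does not state it. Section 3 presents 50 as the whole study population, names one recruiting unit for patients, and describes no eligibility or visit schedule for a further 100 people. The need to reconcile stands, and the power figures are conditional on 50 being the total.

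Other objections carry some weight:

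- Some outcomes and metabolic measures are taken at two or three visits, and averaging them could reduce measurement error. The plan specifies no averaging, so this is a caveat.
- The loss rate is back-calculated, and the covariate and direct-effect cases are assumptions. They show direction and are not needed for the conclusion.
- The result depends on the interval. The percentile bootstrap gives lower power at n = 50, about 15–17% at paths of 0.25 and 43–49% at 0.35. The method the plan names is the more favourable of the two.
- The two hypothesis wordings are partly bridged, because the mediation text lists both anhedonia and reward behaviour as outcomes. That point is secondary.

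**Conclusion.** The concern holds. The plan states both 50 and 116/150, nothing in it says which applies, and no power is given for 50. The derivation of 116 is not at fault.

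If 50 is the total, the mediation test has about 26–60% power for equal paths of 0.25–0.35, or 18–45% after the implied loss. A true mediated effect of the size the plan expects would be missed about 40–74% of the time at n = 50 (1 − 0.60 to 1 − 0.26). A null result would then be inconclusive. These figures rest on one mediator, full mediation, no covariates, an even split and one measurement per person. If 150 is the total, they do not describe the primary test, but Section 3 is then wrong as written. Either way the text must be corrected before a reader can know the enrolment or the power.

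**What to change.** State one total and make Section 3 (Study population, Study Procedures, Neural Circuits Assessment), Section 6 (Power Analysis, Potential Challenges) and Section 7 agree with it. Say whether the crossover and imaging sample is that total or a defined part of it.

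- **If the total is 50:** replace the 116/150/80% text with the power of the mediation test at 50, before and after attrition. State the assumed paths, number of mediators, direct effect and covariates. Say that a null mediation result would be inconclusive. Remove the 150-participant text and the preliminary analysis at n=50. This costs wording only, and the stated power becomes less favourable.
- **If the total is 150:** correct Section 3 and say which analyses use 150 and which use 50. Enrolment is already planned in Section 6, so no participants are added to it. Section 3 gives each participant two scans, however. Applying that to everyone would mean 150 × 2 = 300 scans instead of 50 × 2 = 100, unless a 50-person imaging subsample is defined.

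In either case, bring the primary hypothesis in Sections 1 and 6 to one wording. The choice of primary, and any detectable effect reported for the planned GEE or mediation analysis, is the sponsor's.

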Screening and Baseline Assessment: Patients and healthy controls will first meet, in-person or virtually, with a staff psychiatrist for a clinical consultation or a research team member, respectively. After obtaining consent and if inclusion criteria are met, a medical comorbidity questionnaire will be administered to screen for concurrent and lifetime medical conditions. Participant's demographic characteristics and current medications, as well as lifetime psychotropic medications received will be recorded. We will also assess dietary intake with the Diet History Questionnaire III (DHQ III); smoking, by questioning number of cigarettes smoked per day, age when smoking started, and quitting date, if applicable, to calculate a smoking pack-year history; physical activity using the International Physical Activity Questionnaire (IPAQ); and alcohol and/or substance abuse. In addition, we will assess demographics, socioeconomic status, medical history, and family psychiatric history; childhood trauma history with the Childhood Trauma Questionnaire (CTQ) will also be assessed. Participants will also be asked to complete an MRI screening questionnaire to ensure that they have no contraindications. The following self-reported measures will be carried out: Perceived Deficits Questionnaire-Depression (PDQ-D), Sheehan Disability Scale (SDS), UCLA life Stress (Episodic), DeJong Gierveld Loneliness Scale, and Pittsburg Sleep Quality Index (PSQI) (Table 1).

When in-person visits are possible, participants will complete a urine drug screen. Female participants will be asked to do blood work to confirm they are not pregnant.

Physiological Assessment: Anthropometric (i.e. BMI, waist-hip ratio) and metabolic measurements (i.e. fasting glucose, fasting insulin, glycated hemoglobin, lipids and HOMA-IR) will be completed at each study visit (1-3). In addition, physical activity and energy expenditure will be measured using an accelerometer. Participants must wear the accelerometer at all times for one week and return it upon Visit 3 for data collection and analysis. Additionally, a heart rate monitor device will be connected to the accelerometer that will monitor heart rate variability over one day of the week that the subjects wear the accelerometer.

Laboratory Assessment:

Routine: the following laboratory tests will be completed:

Triglycerides
Total Cholesterol
Insulin
Glucose
HbA1c
C-Peptide
IGF-1
TSH
Free T4
Free T3
C-Reactive Protein
hCG

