This procedure is repeated until the required number of nasal spray bottles has been prepared. Once completed, the nasal spray bottles are wiped with 70% isopropyl alcohol soaked gauge and removed from the laminar flow hood and appropriately labeled.

Both active and placebo nasal spray bottles are kept separate from each other and a worksheet will be completed to document information, including date of preparation, batch #, expiry date, drug name and strength. The IV certified pharmacy technician who has prepared the dose is responsible for completing the documentation and will be affixing the labels identifying what was prepared. The labels, at a minimum, will contain information regarding the lot #, strength, date of manufacture, expiry date, and storage conditions. All of this will be verified by a pharmacist.

Labeling

All labels will contain product name, volume, protocol number, investigational drug warning, dosage instructions, storage conditions, lot number, expiration date, and the pharmacy name.

Storage

Please refer to the pharmacy manual for information on storage.

Study Medication Administration

This will be a single-dose, randomized, double-blinded, cross-over study involving intranasal insulin/placebo solution.

Designated pharmacy staff will dispense study medication, in a double-blind manner, according to the randomization code specific to each subject and dosing period.

Details regarding intranasal insulin and diluent can be referred to in the pharmacy manual.

The investigator and/or designee will instruct the study participant on how the intranasal insulin/placebo spray should be administered. Each study participant is to receive a single dose of Humulin R 160 U / placebo.

- Given:
 - The nasal spray bottles provide a deliverable volume of 0.1 mL/spray.
 - o Humulin R insulin will be sourced as 100 units/mL in a vials of 10 mL from Eli Lilly.
 - o Diluent will be sourced as 10 mL/vial from Eli Lilly.
- Each spray will offer:
 - o 0.1 mL (i.e., 10 units) of Humulin R insulin
 - o 0.1 mL of diluent (to serve as placebo)
- To obtain a dose Humulin R 160 U / placebo
 - o 16 sprays (0.1 mL/spray) are to be given per dose

- o This works out to 16 sprays split between each nostril such that each nostril receives 8 sprays.
- The sprays will be administered between alternating nostrils.

Given this is a crossover study, the study participants will receive a total of two doses in this study. The time between 2 doses is one week.

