An adverse event is the development of an undesirable medical condition or the deterioration of a pre-existing medical condition following or during exposure to a pharmaceutical product, whether or not considered causally related to the product. An undesirable medical condition can be symptoms (e.g., nausea, chest pain), signs (e.g., tachycardia, enlarged liver) or the abnormal results of an investigation (e.g., laboratory findings, electrocardiogram). In clinical studies, an AE can include an undesirable medical condition occurring at any time, including run-in or washout periods, even if no study treatment has been administered.

Serious adverse event

A serious adverse event is an AE occurring during any study phase (i.e., run-in, treatment, washout, follow-up), and at any dose of the investigational product, comparator or placebo, that fulfils one or more of the following criteria:

- results in death
- is immediately life-threatening
- requires in-patient hospitalization or prolongation of existing hospitalization
- results in persistent or significant disability or incapacity
- is a congenital abnormality or birth defect
- is an important medical event that may jeopardize the patient or may require medical intervention to prevent one of the outcomes listed above.

The causality of SAEs (i.e., their relationship to study treatment) will be assessed by the investigator(s). Note that SAEs that could be associated with any study procedure should also be reported. For such events the casual relationship is implied as "yes".

Recording of adverse events

AEs will be collected during each visit. At each visit, subjects will be asked if they have had any health problems since the previous visit. All AEs will be recorded appropriately, whether or not considered related to the investigational product. This will include AEs spontaneously reported by the patient and/or observed by the staff as well as AEs reported in response to a direct question e.g. "Have you had any health problems since your last visit?"

For each AE, the following parameters be described:

- start and stop date
- action taken with regards to investigational product
- outcome
- if the AE caused the patient to discontinue
- a statement if the AE fulfils the criteria for a SAE or not
- the investigator's assessment of the causal relationship between the event and the investigational product
 - intensity of the AE
 - o mild (awareness of sign or symptom, but easily tolerated)

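### No adverse-event contact is scheduled after the second dose, so the two crossover doses are observed over unequal solicited windows

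*Combined protocol and SAP*

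**What the plan says.** Under Recording of adverse events, the protocol states that "AEs will be collected during each visit", and then: "At each visit, subjects will be asked if they have had any health problems since the previous visit". A passive route is also kept: "This will include AEs spontaneously reported by the patient and/or observed by the staff".

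Table 1 in Section 3 has three visit columns: "Assessment Baseline (V1) First Spray (V2) Second Spray (V3"). The Physiological Assessment paragraph counts the visits the same way, with measurements that "will be completed at each study visit (1-3"), and has the accelerometer returned at Visit 3. Section 4.1 states: "Given this is a crossover study, the study participants will receive a total of two doses in this study", with one week between them.

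On dosing days, Section 3 provides glucose and cardiovascular monitoring at the start of imaging. Plasma glucose and insulin are sampled at spray administration and straight after the scan.

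The definition of a serious event reads: "A serious adverse event is an AE occurring during any study phase (i.e., run-in, treatment, washout, follow-up"). Follow-up of events is left to the investigator's judgement, with no fixed time. The available text schedules no visit, call or other contact after V3.

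**The concern.** The only solicited AE question looks backwards from one visit to the one before. That works for a dose followed by another visit. The second dose is given at the last visit, so nobody is scheduled to ask about it once the participant has gone home.

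Three things are at stake. First, mild or moderate events that begin or are noticed after leaving V3 will be recorded only if the participant volunteers them. Second, each AE record must carry a stop date and an outcome, yet no scheduled contact exists to obtain these for an event still ongoing when V3 ends. Third, any listing of events by period would set a period with about a week of solicited observation beside one with only a visit, so a difference between periods could be an artefact of the asking.

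**Working it through.** The plan states no figure for AE ascertainment, so there is none to reproduce. The check is a comparison of the AE text with the schedule, followed by a count of exposures.

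**What each question covers**

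- V1: no earlier study visit and no dose.
- V2: looks back to V1, before any dose.
- V3: looks back to V2, so it covers the first dose over about one week.
- After V3: no question. The second dose is covered by observation on site, up to the post-scan blood sample, and by unprompted reports.

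One of each participant's two doses therefore gets a solicited after-visit question.

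**How many insulin doses are affected**

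Inputs: one insulin and one placebo dose per participant (Section 4.1); N = 50 (Section 3) or 150 (enrolment goal, Section 6). The share s receiving insulin second is not given, because Section 5 defers assignment to the pharmacy manual; s = 1/2 is assumed.

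Insulin doses without a solicited after-visit question = N × s.

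| | N = 50 | N = 150 |
|---|---|---|
| s = 1/2 | 25 of 50 | 75 of 150 |
| 95% range under unrestricted 1:1 randomisation, Binomial(N, 1/2) | 18 to 32 | 63 to 87 |
| s from 1/3 to 2/3 | about 17 to 33 | 50 to 100 |

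The placebo count is N × (1 − s), which is again 25 of 50 or 75 of 150 at s = 1/2.

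**Effect on the insulin–placebo comparison**

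Let a be the chance that an after-visit event is recorded when the question is asked, and b the chance when it is not, the same for both conditions. At s = 1/2 the average chance is (a + b)/2 for insulin and (a + b)/2 for placebo. The factor is common, so neither condition is favoured in expectation. If b is below a, the recorded count is lower for both than if everyone were asked.

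**Information lost on after-visit events, N = 50**

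For n solicited insulin doses, treating the unsolicited ones as giving no information:

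- Exact one-sided 95% upper bound with zero events = 1 − 0.05^(1/n). For n = 25: 11.3%. For n = 50: 5.8%.
- Chance of at least one event at true rate p = 1 − (1 − p)^n. For p = 5%: 72% with n = 25, 92% with n = 50. For p = 2%: 40% with n = 25, 64% with n = 50.

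At N = 150 the zero-event bound moves from 3.9% (n = 75) to 2.0% (n = 150).

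**The case against.** The strongest reply is that the second dose is not unobserved. Spontaneous and staff-observed events are recorded, serious events are defined for any study phase and must be reported, and the dosing visit includes glucose and vital-sign checks. This stands. A reader might infer that nothing at all is ascertained after V3, and the text does not support that. What is missing is scheduled, solicited questioning. The events most likely to be volunteered are the serious ones, so the gap bears mainly on lesser events.

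A reader might also infer that insulin is made to look safer than placebo. Under 1:1 sequences it is not, because both conditions lose the same share. No AE rate is among the aims in Section 1 or the analyses in Section 6, so no planned analysis is invalidated.

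Nor can a percentage under-count be stated. It would need the share of events arising after participants leave and the rate of unprompted reporting, and the documents give neither.

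A contradiction over the follow-up phase named in the serious-event definition is tempting too. The same parenthesis lists a run-in, which this trial also lacks, so the wording looks generic. It needs tidying but proves little.

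Finally, the documents show no particular late risk. Section 3 describes the intranasal route as having no relevant effect on peripheral glucose. The 12-hour fast is a rule for blood collection; nothing says participants are still fasting when dosed or when they leave.

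None of this supplies a solicited question after the second dose.

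**Conclusion.** The point holds as a gap in safety ascertainment. Followed as written, the plan gives the first dose about a week of solicited AE observation and the second only the V3 visit plus unprompted reports. Under 1:1 sequences, about half of the insulin doses and half of the placebo doses are affected. After-visit events are under-ascertained for both conditions and the two periods are not comparable, but the insulin–placebo contrast is not biased in expectation. The main behavioural and imaging analyses are untouched.

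The size rests on an assumed 1:1 ratio and on which sample size applies, since 50 and 150 both appear. The bounds and detection probabilities also treat unsolicited doses as uninformative, so they overstate the loss to the extent that participants report unprompted. The pharmacy manual and the text following the heading of Section 8 were not available; a contact defined only there could not be checked.

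**What to change.** Add to Table 1 and to Recording of adverse events one telephone or online contact after V3, at the interval that separates V2 from V3 (one week), using the same health-problems question. The interval is chosen to equalise the two windows; the documents do not show that a single dose needs exactly that long.

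State that AE and SAE collection, including the follow-up phase named in the serious-event definition, ends at that contact. List AEs by the condition last received, over these equal windows.

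At N = 50 under 1:1 sequences, insulin doses with a solicited after-visit question rise from 25 to 50 if every participant is reached. The cost is one short call per participant and a small amendment, with no added visit, procedure or assessor. A few participants will be unreachable; their number should be reported.
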